4 STUDY ENDPOINTS

4.1 Parent study

4.1.1 Primary endpoint

The primary efficacy endpoint is based on the blinded raters' Clinical Impression of Change in Severity (CI-CS) score on either the 9 Hole Peg Test of the Dominant Hand (9HPT-D) or the 8 Meter Walk Test (8MWT). The primary endpoint is defined as the CI-CS comparing the end of treatment (Visit 4) with baseline (Visit 2) **minus** the CI-CS comparing the end of washout (Visit 6) with the end of treatment (Visit 4).

4.1.2 Key secondary efficacy endpoints

Supportive secondary endpoints that directly supplement the analysis of the primary endpoint will be evaluated as follows:

- The individual components of the primary endpoint, that is the CI-CS from Visit 2 to Visit 4 and the CI-CS from Visit 4 to Visit 6.
- Difference in the blinded rater's Clinical Impression of Severity (CI-S) values from baseline (average of Visit 1 and Visit 2) to end of treatment (average of Visit 3 and Visit 4) and from end of treatment (average of Visit 3 and Visit 3 and Visit 4) to end of washout (average of Visit 5 and Visit 6).

Clinical Study Reference: IB1001-202

- Measurement of change in performance of the CI-CS score of either the 9HPT-D or the 8MWT reclassified to a 3-point scale.
- An evaluation of the CI-CS for the test (9HPT-D or 8MWT) that was not selected as the primary anchor test.

4.1.3 Additional secondary efficacy endpoints

For all additional secondary endpoints, the change from Visit 2 to Visit 4 and the change from Visit 4 to Visit 6 will be evaluated.

Measurement of Ataxia and Functioning

- Spinocerebellar Ataxia Functional Index (SCAFI). The SCAFI is composed of the 8MWT, the 9HPT, and the PATA rate, a measure of speech performance.
- Scale for Assessment and Rating of Ataxia (SARA) score. SARA has 8 items that are related to gait, stance, sitting, speech, finger-chase test, nose-finger test, fast alternating movements and heel-shin test.

Measurement of Health-related Quality of Life

• Quality of Life EQ-5D-5L for patients aged ≥18; EQ-5D-Y for children aged 6-17 years (two parts: the EQ visual analogue scale (EQ-VAS) and the EQ descriptive system).

Measurement of Overall Neurological status

• Modified Disability Rating Scale (mDRS) The scores of the six components (ambulation, language, manipulation, swallowing, seizures, and ocular movement) of this scale add up to a composite value.

Measurement of Global Impression

- Clinical Global Impression of Severity by the treating physician (CGI-S-physician) at every visit.
- Clinical Global Impression of Change by the treating physician (CGI-C-physician) comparing end of treatment (Visit 4) to baseline (Visit 2), and end of washout (Visit 6) to end of treatment (Visit 4).
- Clinical Global Impression of Severity by the caregiver (CGI-S-caregiver) at every visit.
- Clinical Global Impression of Change by the caregiver (CGI-C-caregiver) comparing Visit 4 to Visit 2 and Visit 6 to Visit 4.
- Clinical Global Impression of Severity by the patient (CGI-S-patient) at every visit *if they are able.*
- Clinical Global Impression of Change by the patient (CGI-C-patient) comparing Visit 4 to Visit 2 and Visit 6 to Visit 4 *if they are able*.

The CGI-S scales are on a 7-point scale ranging from 'normal, not ill at all' to 'among the most ill patients'. The CGI-C scales are also on a 7-point scale ranging from 'very much improved' to 'very much worse'.

4.1.4 Exploratory endpoints

Sparse PK sampling will be collected for biochemical analysis so to characterize the pharmacokinetics of N-Acetyl-L-Leucine in patients with GM2 Gangliosidosis.

Clinical Study Reference: IB1001-202

(Note that analysis and reporting of pharmacokinetics is outside the scope of this analysis plan. PK data handling, analysis and reporting will be done by an external company that specializes in PK analysis and reporting. The PK report will be added to Appendix 16.1 of the CSR as a separate document.)

4.1.5 Safety endpoints

The safety parameters to be evaluated are:

- Adverse Events
- Laboratory safety measurements: haematology, clinical chemistry, urinalysis
- Vital signs
- Electrocardiography (ECG)

4.2 Extension phase

With respect to the Parent study, all endpoints for the Extension phases are considered secondary to the endpoints of the Parent study phase.

4.2.1 Primary endpoint

The primary endpoint in the Extension phase is "success" based on the mDRS score, with success defined as no change or improvement (decrease) in the mDRS score from Visit 7 to Visit 9.

4.2.2 Secondary efficacy endpoints

Supportive secondary endpoints for the Extension phase that directly supplement the analysis of the primary endpoint for the Extension phase will be evaluated as follows:

• Full PK sampling at Visit 7 and Visit 9 to characterize the pharmacokinetics of N-Acetyl-L-Leucine in patients with GM2 Gangliosidosis. (Note that analysis and reporting of pharmacokinetics is outside the scope of this analysis plan. PK data handling, analysis and reporting will be done by an external company that specializes in PK analysis and reporting. The PK report will be added to Appendix 16.1 of the CSR as a separate document.)

4.2.3 Exploratory Endpoints

Exploratory endpoints will investigate other measures of symptoms and quality of life from Visit 7 to Visit 9 for the following measures:

Measurement of Ataxia and Functioning

- Spinocerebellar Ataxia Functional Index (SCAFI). The SCAFI is composed of the 8MWT, the 9HPT, and the PATA rate, a measure of speech performance.
- Scale for Assessment and Rating of Ataxia (SARA) score. SARA has 8 items that are related to gait, stance, sitting, speech, finger-chase test, nose-finger test, fast alternating movements and heel-shin test.

Measurement of Health-related Quality of Life

• Quality of Life EQ-5D-5L for patients aged ≥18; EQ-5D-Y for children aged 6-17 years (two parts: the EQ visual analogue scale (EQ-VAS) and the EQ descriptive system).

Clinical Study Reference: IB1001-202

Measurement of Global Impression

- Clinical Global Impression of Severity by the treating physician (CGI-S-physician).
- Clinical Global Impression of Change by the treating physician (CGI-C-physician).
- Clinical Global Impression of Severity by the caregiver (CGI-S-caregiver).
- Clinical Global Impression of Change by the caregiver (CGI-C-caregiver).
- Clinical Global Impression of Severity by the patient (CGI-S-patient) if they are able.
- Clinical Global Impression of Change by the patient (CGI-C-patient) *if they are able.*

The CGI-S scales are on a 7-point scale ranging from 'normal, not ill at all' to 'among the most ill patients'. The CGI-C scales are also on a 7-point scale ranging from 'very much improved' to 'very much worse'.

Videos of the primary and non-primary anchor tests are collected throughout the extension phase for the CI-CS. These videos may be analyzed in order to inform the development and validation of the CI-CS.

4.2.4 Additional exploratory endpoints

For all additional exploratory endpoints, the change from Visit 7 to Visit 10, Visit 9 to Visit 10 and Visit 10 to Visit 12 may also be evaluated. In addition, the change from Visit 1 to Visit 12 may also be investigated.

- SCAFI
- 9-HPT of dominant hand
- 8MWT
- SARA
- Health-related Quality of Life (EQ-5D-5L/Y)
- CGI-S by physician
- CGI-S by caregiver
- CGI-S by patient *if able*
- CGI-C by physician
- CGI-C by caregiver
- CGI-C by patient *if able*
- mDRS

4.2.5 Safety endpoints

The safety parameters to be evaluated are:

- Adverse Events
- Laboratory safety measurements: haematology, clinical chemistry, urinalysis
- Vital signs
- ECGs
- Physical Examination

Clinical Study Reference: IB1001-202

5 PARENT STUDY: STATISTICAL ANALYSIS

5.1 General considerations

The Parent study is considered the study period between screening (Visit 0 or Visit 1) through Visit 6.

Raw data (in listings) will be presented in the same precision as received. Appropriate rounding will be performed for the following summary statistics, where applicable: mean, standard deviation (SD) and two-sided 90% confidence limits will be presented with at least one more decimal than the original data; minimum and maximum values will be presented with the same precision as the original data. In frequency tables, percentages will be presented with 1 decimal unless otherwise stated.

P-values will be presented with 3 decimals, and those smaller than 0.001 will be replaced by <0.001. One-sided p-values smaller than 0.05 will be considered statistically significant for the primary endpoint and indicative for other endpoints. No adjustment for multiple comparisons will be applied. Conclusions regarding treatment efficacy will not solely rely on detecting statistical significance but equal emphasis will be placed on the magnitude and clinical relevance of treatment differences as judged by the point estimates. All evaluations other than the primary endpoint will be considered exploratory in nature.

Descriptive statistics presented in general summary tables will be the number of non-missing observations (n), mean, SD, minimum, median and maximum for quantitative data. For categorical data, frequency counts and percentages will be determined.

In general, baseline is defined as the value measured prior to first study treatment administration (at Visit 2), unless otherwise specified. In case no value at Visit 2 is available, the value measured at Visit 1 will be used. A footnote may be added to those tables/listings presenting baseline value, with an explanation how this value was assessed.

If available in the database, data for screening failures will not be presented in summary tables, except for disposition, medical history and end-of-study displays. Data for screening failures will be listed as available.

A treatment emergent adverse event (TEAE) is defined as an adverse event that appears during or after study treatment and was absent before.

5.2 Adjudication of endpoint data

Each individual video (CI-S) or video pairing (CI-CS) will be read by two independent reviewers. For the CI-S assessments of the primary and non-primary anchor test, the independent raters will be given 6 videos of the patient's performance taken at Visit 1 to Visit 6. For the CI-CS assessments of the primary and non-primary anchor test, the raters will be given three pairs of videos and asked to score the CI-CS for each video pair. The video pairs will be labeled Video A to Video B, Video B to Video C, and Video C to Video A¹. The videos will be presented in a random order, and the independent raters will be blinded to the timepoint corresponding to each video. The appropriate Likert scale score will be provided to each of the videos and pairs of videos.

^{(2019).} Video Review Charter. IntraBio Ltd. Internal Document.

Clinical Study Reference: IB1001-202

For the CI-CS assessment, pairs of videos will be evaluated with the Likert scale defined as:

- Significantly Improved (Score = +3)
- Much Improved (Score = +2)
- Minimally Improved (Score = +1)
- No Observable Change (Score = 0)
- Minimally Worse (Score = -1)
- Much Worse (Score = -2)
- Significantly Worse (Score = -3)

If there is a scoring difference between the two blinded raters for a CI-CS assessment, the following rules will apply:

- If the difference between the blinded raters is 1, the two scores will be averaged, and the unrounded average value will be used for further analysis.
- If there is a scoring difference of >1 between the two blinded raters for a CI-CS assessment, then a third blinded rater will review the scores and will determine which score is more accurate (adjudication by consensus). The adjudicator's decision will be the final score for that video assessment and used for further analysis.

For the CI-S assessment, individual videos will be evaluated with the Likert scale defined as:

- Normal, not at all ill (Score = +3)
- Borderline ill (Score = +2)
- Mildly ill (Score = +1)
- Moderately ill (Score = 0)
- Markedly ill (Score = -1)
- Severely ill (Score = -2)
- Among the most extremely ill patients (Score = -3)

If there is any scoring difference between the two blinded raters for a CI-S assessment, the two scores will be averaged, and the unrounded average value will be used for further analysis.

Note that in averaging situations for the CI-CS and CI-S assessments, the scores may not fit the Likert scales as mentioned above. In case of average scoring present in the database, presentations will be on score only, without the additional description.

5.3 Missing data

Patients that withdraw from the study are replaced at the discretion of the sponsor. Data from withdrawal patients will be included in the analysis until their last assessment.

For handling missing data of the statistical analyses applied to the primary and key secondary endpoints, refer to the respective analysis sections.

For other endpoints being presented with descriptive statistics only, such as baseline/screening data, safety presentations, additional secondary endpoints and (additional) exploratory endpoints, no imputation will be performed, unless otherwise specified (in the respective analysis section or in Section 10.1). All these analyses will be performed on data available at the visit considered. In summary tables, the number of patients without missing data will be presented (per visit, if

Clinical Study Reference: IB1001-202

applicable) unless otherwise specified. In calculations of percentages, subjects with missing data will not be considered in numerator or denominator unless otherwise specified.

Using the most conservative approach, missing/incomplete information related to AEs will be handled as listed below, to indicate an AE as being treatment emergent or presented having a certain intensity/causality. Note that the imputed dates or intensity/causality will not appear in data listings, but only in descriptive statistics tables (where applicable).

- In case of (partially) missing onset dates, the AE will be handled as follows:
 - If full start date is available, and on or after first dosing date, the AE is considered treatment emergent.
 - In case full stop date is available and prior to first dosing date, the AE is considered prior.
 - If the day part of the start date is missing:
 - The AE is considered treatment emergent if the month and year of the start date are the same or after the month and the year of the first dosing date.
 - If the day and month part of the start date are missing:
 - The AE is considered treatment emergent if the year of the start date is the same or after the year of the first dosing date.
 - In case the start date is completely missing:
 - If stop date is fully available and on or after the first dosing date, the AE is considered treatment emergent.
 - If the stop date is partially missing, but the month and year (or year alone in case of missing month) are after the month and year (or year alone) of the first dosing date, the AE is considered treatment emergent.
 - In case full start date and full stop date are missing, the AE is considered treatment emergent.
- In case intensity is missing for a certain TEAE, this will be regarded as severe.
- In case causality is missing for a certain TEAE, this will be regarded as related.
- In case seriousness is missing for a certain AE, this is discussed and addressed prior to database lock and unblinding in agreement with the sponsor and data management provider.

Regarding prior/concomitant medication, a similar approach will be followed for partially missing dates, as will be done for AEs as described above. If a comedication is started and stopped prior to the first date of study treatment (i.e. first dosing date), this is considered prior.

Based on the BDRM, certain values can be decided to be excluded from analyses. These values will be listed, but not included in descriptive statistics, plots or statistical analyses. This may be outlier data that are a result of unambiguous measurement errors.

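### SAP 5.3 leaves an adverse event with no start date, and a stop date known only to the month or year of first dose, outside every classification rule, contrary to its stated conservative approach

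*SAP*

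**What the plan says.** SAP 5.3 opens its rules with a principle: "Using the most conservative approach, missing/incomplete information related to AEs will be handled as listed below". The rules that follow are:

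- **Full start date:** treatment emergent if on or after first dose.
- **Start day missing:** counted as treatment emergent when "the month and year of the start date are the same or after the month and the year of the first dosing date".
- **Start day and month missing:** treatment emergent if "the year of the start date is the same or after the year of the first dosing date".
- **Start date completely missing, full stop date:** "If stop date is fully available and on or after the first dosing date, the AE is considered treatment emergent".
- **Start date completely missing, partial stop date:** treatment emergent if the known stop month and year, or year alone, "are after the month and year (or year alone) of the first dosing date".
- **Both dates missing:** "In case full start date and full stop date are missing, the AE is considered treatment emergent".
- **Prior events:** "In case full stop date is available and prior to first dosing date, the AE is considered prior". This is the only rule in the list that makes an event prior.

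SAP 5.7.1 builds the summary tables from TEAEs, lists all AEs, and requires that listing to separate prior from treatment-emergent events. SAP 6.3 applies similar handling to the Extension phase, with first dose redefined for each extension period. SAP 5.3 also applies a similar approach to partial dates of prior and concomitant medication.

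**The concern.** Four of the five date comparisons that can make an event treatment emergent include the tie. The fifth, for a partial stop date, excludes it. Two patterns then have no home: start unknown with a stop in the first-dose month (day missing), and start unknown with a stop in the first-dose year (month and day missing).

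The result is perverse. If the site records neither date, the event is treatment emergent. If the site adds that it ended some time in the first-dose month or year, no rule makes it so, even though that information does not exclude onset after dosing. A programmer who codes the bullets as written would leave such events out of the TEAE tables, and could not place them in the split that SAP 5.7.1 requires in the listing.

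**Working it through.** No figure in the plan depends on this rule, so there is nothing to reproduce. The check is to apply the bullets literally and then ask what the affected records could be.

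**Step 1. The rule applied literally.** Illustrative first dose 15 June 2020, start date completely missing:

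| Stop date recorded | Outcome under SAP 5.3 | With equality allowed |
|---|---|---|
| none | treatment emergent | unchanged |
| 20 June 2020 | treatment emergent | unchanged |
| 15 June 2020 | treatment emergent | unchanged |
| 10 June 2020 | prior | unchanged |
| July 2020 | treatment emergent | unchanged |
| **June 2020** | **no rule applies** | **treatment emergent** |
| May 2020 | no rule applies | unchanged |
| 2021 | treatment emergent | unchanged |
| **2020** | **no rule applies** | **treatment emergent** |
| 2019 | no rule applies | unchanged |

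The May 2020 and 2019 rows are also unassigned, but those events ended before first dose and plainly are not treatment emergent. The two bold rows are the problem.

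**Step 2. Could the bold rows be treatment emergent?** Yes. A stop in June 2020 is compatible with onset on any day from 15 to 30 June. A stop in 2020 is compatible with onset from 15 June to 31 December. The SAP already accepts possibility as its standard elsewhere: a stop on 20 June with no start date is counted, although the event may have begun before 15 June.

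**Step 3. How likely is post-dose onset?** The documents do not say, so this needs assumptions.

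- *From the documents:* AEs are recorded from consent (Protocol 6.2.1). The schedules put first dose at Day 1 and Visit 6 at Day 84, with consent at Day -14 for naïve and Day -56 for non-naïve patients.
- *Assumed:* first-dose dates spread evenly over a calendar year; onset even from consent to Day 84; exponential event duration with mean 3, 7 or 14 days.

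| Share with onset on or after first dose | Naïve | Non-naïve |
|---|---|---|
| Stop known to be in first-dose month | 0.44 to 0.54 | 0.26 to 0.44 |
| Stop known only to be in first-dose year | 0.84 | 0.58 to 0.59 |

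So, of the same-month events that the amended rule would count, the share with pre-dose onset is 1 - 0.54 = 0.46 to 1 - 0.44 = 0.56 for naïve patients, and 1 - 0.44 = 0.56 to 1 - 0.26 = 0.74 for non-naïve patients.

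**The case against.** The case for leaving the text alone has four parts.

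- **The SAP does not declare these events non-treatment-emergent.** Correct. It assigns them nothing, and exclusion is only what follows from literal coding. One could also read the last bullet as covering any event with neither date complete, which would rescue them. That reading makes the partial-stop branch redundant, and SAP 10.1 uses the corresponding phrase, under GM2 diagnosis, for a date that is wholly absent. If it is what the sponsor means, the text still needs correcting.
- **Other routes exist.** SAP 10.1 lets unforeseen conventions be settled when met, SAP 3.4 provides a data review meeting before database lock, and Protocol 9.1 and 9.2 have discrepancies queried until resolved. These should make such records rare. They do not correct a comparison that is written down and would be followed.
- **The events remain visible.** They stay in the listing of all AEs, and serious events and deaths have separate listings. That limits the harm.
- **A same-month stop is weak evidence of post-dose onset.** This stands, and it is why the point rests on possibility.

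Two stronger readings are tempting and should be resisted. A reader might infer that the dropped events most likely occurred on drug, since 84/(14 + 84) = 84/98 = 86% of a naïve patient's recording window follows first dose. That figure suits only naïve patients with year-only stops and even onset, and it includes washout. Time on drug is 42/98 = 43%; for non-naïve patients the shares are 84/140 = 60% after first dose and 42/140 = 30% on drug. Washout onsets do still meet the TEAE definition in SAP 5.1, so the error lies in saying on drug. A reader might also argue that, because a stop cannot precede its onset, the stop-date rule must be at least as inclusive as the start-date rule. It does not follow: a stop in the first-dose month allows onset in that month or earlier, whereas a start in that month fixes onset there.

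**Conclusion.** The text is wrong as written, at low priority. One branch of SAP 5.3 departs from the conservative principle that introduces it and from the treatment of ties in every parallel comparison. Two date patterns are left unclassified, and literal programming would omit possible TEAEs from the tables.

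That conclusion needs only the SAP wording; the shares in the working rest on assumed onset and duration patterns and serve only to gauge the cost of the fix. The documents give no count of affected records. Few are likely, because an event needs both a wholly missing start date and a partial stop date that ties with first dose. No efficacy or sample-size result is touched.

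**What to change.** In the SAP 5.3 branch for a completely missing start date and a partial stop date, replace the strict comparison so that the stop month and year (or year alone) *are the same as or after* those of first dose. Only the two bold patterns change. SAP 6.3 then carries the amendment to both extension periods; the similar handling of medication dates should be checked for the same gap.

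An optional closing line would complete the rule: an event is treatment emergent unless the available date parts show that it started or ended before first dose. This also settles stops in an earlier month or year.

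The cost is a few words in the SAP and one operator in the program. The downside is that some events with pre-dose onset, possibly about half or more of the same-month cases under the assumed durations, will be counted as treatment emergent. A conservative rule accepts that, and a footnote to the TEAE tables giving the number of events classified from incomplete dates would let a reader judge its effect.
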